All of the studies described here were primarily treating patients with IC. Only Jakubseviciene et al. (2014) and Badger et al (2007) included patients with PAD and rest pain. **To date, there are no studies dedicated to patients with critical limb ischemia comparing outcomes for exercise training versus BMT post revascularization.** All of these studies exclusively evaluate patient-related outcomes such as walking distance, functional capacity and QoL. While these parameters are tremendously important, there are no data regarding how post treatment exercise training may affect amputation rates, readmission to hospital or reintervention rates in the PAD patients with critical limb ischemia. Such parameters are defined as major adverse limb events (MALE).

Health Economics

The 1992 Canadian Heart Health survey showed a significant economic benefit for all participants who participated in an exercise program, both supervised and unsupervised. In patients with known cardiovascular disease, a SEP showed significant cost savings for years of life (Lowenstein, Coupal, Zowall, & Grover, 2000). In patients with IC, studies have shown that SEP is more cost- effective than endovascular interventions as a primary treatment modality. Furthermore, although the initial cost of SEP may be slightly greater when compared with HEP, it has greater cost-effectiveness up to five years (Fokkenrood et al., 2014; Reynolds et al., 2014; Spronk et al., 2009). There has been no data evaluating the cost benefits associated with CLI patients who have undergone revascularization. Given that re-interventions are frequent (and costly), post revascularization exercise training may be of significant and substantial benefit in patients with CLI.

Summary

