Exercise training is a proven effective treatment for patients with PAD with significant functional, psychosocial and economic benefits. In current practice, there are no guidelines for exercise training and rehabilitation for patients who have progressed to CLI and have undergone revascularization. While it may be a challenge given the severity of disease and number of comorbidities in this patient population, it is great a disservice to deny these patients exercise rehabilitation given the possible advantages for their functional capacity, quality of life and even survival. Randomized controlled trials (RCT) are necessary to determine the precise role of exercise rehabilitation in patients with CLI. An RCT will provide guidance for regarding exercise tolerance, appropriate exercise modalities as well as the challenges and benefits of exercise rehabilitation in this critically ill population.

Objectives:

The aim of this pilot study is to develop a better understanding of the role for supervised exercise rehabilitation programs (SEP) in CLI patients after revascularization.

Our key objectives are as follows:

- 1) Our primary objective is to show that a 12-week SEP will improve functional capacity and quality of life in patients with CLI after revascularization. We will assess the feasibility for completion of a 12-week SEP in patients with CLI who have undergone revascularization.
- 2) Our secondary objective is to monitor major adverse limb events (MALE) and survival in patients who complete a 12-week SEP after revascularization.

Hypotheses:

- 1) We hypothesize that PAD-CLI patients who participate in an exercise rehabilitation after they have undergone revascularization will have a greater improvement in functional capacity and quality of life compared with patients treated with best medical therapy alone.
- 2) We hypothesize that PAD-CLI patients who participate in an exercise rehabilitation after they have undergone revascularization will have fewer MALE and improved survival compared with patients treated with best medical therapy alone.

OUTCOME MEASURES:

Primary outcome measures:

Our primary outcome measure for this project will be change in functional capacity as measured by a 6-minute walking test (6MWT) or maximal pain-free walking distance on a treadmill.

Secondary outcome measures:

- 1) Quality of life based on questionnaires validated for patients with PAD, the SF-36 and VQ6
- 2) Completion of a 12 week supervised exercise program

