- 2) Freedom from MALE
- 3) Target vessel and/or bypass patency
- 4) Survival at 1, 3 and 5 years

STUDY DESIGN

This study is a two phase, single-center, non-blinded randomized controlled trial. The first phase of the trial will include 20 patients; 10 assigned to post-operative exercise rehabilitation and 10 to best medical therapy. The primary objective of Phase I is to assess for feasibility and safety of this randomized controlled trial in CLI patients after revascularization. We will assess rate of enrollment, adherence to the exercise regimen and any unforeseen barriers or challenges that patients may encounter with the rehabilitation program.

If Phase I of the trial confirms that the exercise program is feasible and safe for CLI patients post-revascularization, we will proceed with Phase II of the trial. The primary objective for Phase II is to determine if a supervised exercise rehabilitation program will improve walking distance after revascularization compared with patients treated with best medical therapy. Phase II will also compare quality of life outcomes between the two groups.

STUDY POPULATION

The population to be studied in this group is patients with PAD and CLI Fontaine classification III and IV. This means that these patients will have ischemic rest pain in their legs and/or non-healing ischemic ulcers on their feet.

ENROLLMENT

Patients will be identified on a referral basis through our outpatient vascular surgery clinic. The seven practicing vascular surgeons in Calgary will be informed of the current study. Patients who have undergone revascularization for CLI will be identified for consideration of participation in this study within six months of their procedure. All surgical and ischemic wounds to be deemed sufficiently healed prior to assessment for fitness in the study. Once the attending vascular surgeon considers the patient fit to participate, the research coordinator will assess the patient for possible inclusion in the study.

Inclusion Criteria

- 1) Ambulating prior to procedure
- 2) Living independently prior to procedure
- 3) Available to attend all SEP and follow-up appointments
- 4) PAD Fontaine class III and IV (rest pain and tissue loss)
- 5) Entry with consent of vascular surgeon
- 6) Ischemia secondary to TASC A-D lesions identified on imaging (CTA or angiogram)
- 7) Able to understand and sign informed consent
- 8) >18 years of age

Exclusion Criteria

- 1) Confined to wheelchair

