- 2) Patients with exercise tolerance limitations due to other co-morbidities such as cardiorespiratory, musculoskeletal, or peripheral neuropathy. (NYHA class III and IV)
- 3) PAD Fontaine class I and II (asymptomatic, claudication)
- 4) Patients with ongoing tissue loss that limits ambulation
- 5) Patient with previous revascularization procedures
- 6) Patients undergoing revascularization for acute limb ischemia events

SAMPLE SIZE

There are currently no data evaluating outcomes of post-revascularization supervised exercise programs in patients with critical limb ischemia, however these studies have been completed in claudication

patients. Studies on PAD claudication (Fontaine class II) patients who have undergone revascularization followed by SEP have all shown significant improvement in functional capacity compared with best medical therapy alone. These previous studies that showed consistently a 20% greater increase in walking distance in the post-revascularization SEP group compared with Best Medical Therapy (BMT) post-revascularization. Given this previous data, 64 patients are required to have a 80% chance of detecting, with a two-sided significance of 0.05, an increase in the primary outcome measure of a 20% greater increase in distance for the 6MWT in the experimental group compared with the control group. Final sample size will be adjusted for expected attrition.

METHODS

INTERVENTION

Patients included in the study will be identified in the vascular surgery outpatient clinic or through Emergency department as requiring revascularization secondary to critical limb ischemia. Patients will be approached regarding study participation prior to the revascularization procedure. After eligibility is confirmed and patients have signed informed consent, patients will be randomized to one of two groups:

- 1) Best Medical Therapy (BMT)
- 2) BMT + Supervised Exercise Program (SEP)

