The patient will undergo the revascularization procedure and any adjunctive treatment such as wound care/debridement or minor amputation (toes, trans-metatarsal amputation). All surgical wounds and ischemic ulcers will require assessment by attending surgeon for adequate healing prior to initial assessment at the exercise facility. This may require as little as one week or as long as 6 weeks to achieve sufficient healing. The exercise assessment and program delivery will take place at a cardiac rehabilitation facility that has extensive experience in managing patients with cardiovascular disease and PAD in the post op setting.

Best medical therapy

All patients in the study will be assessed and monitored by internal medicine specialists as well as the vascular surgery team for management of PAD risk factors including, but not limited to: hypertension, smoking cessation, dyslipidemia and diabetes. The patients will be prescribed appropriate pharmacotherapy as deemed appropriate. A typical regimen for these patients may include antiplatelet agents, B-blockers, ACE-inhibitors, and diabetic control agents. Patients will be advised to target a systolic blood pressure of $\leq 140\text{mmHg}$ ($\leq 130\text{mmHg}$ if diabetic), $\text{LDL-C} < 2.0\text{ mmol/L}$ and a $\text{HbA1c} \leq 7\%$. They will also be given information regarding engaging in exercise and physical activity three to five times per week. Patients will be asked to keep a log of their physical activity for the 12-week duration of the study. The patients will be provided with a log to record their physical activity.

Standardized Exercise Program Regimen

In addition to best medical therapy management, the patients randomized to the SEP arm of the trial will attend a supervised exercise program at a cardiac rehabilitation facility at least two times per week for 12 weeks. Programs will be designed and coordinated by an exercise physiologist. All patient expenses for the program will be covered by the study budget. There will be no financial burden placed on the participants.

MEASUREMENTS

General health metrics will be collected at the start and end of the 12-week intervention period. This includes height, weight, BMI, blood pressure and resting heart rate. We will record medications,

smoking history status, presence of diabetes, dyslipidemia, cardiovascular disease history including previous myocardial infarct (MI) and stroke/transient ischemic attack.

PRE/POST TESTING

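### MALE is defined only in the Background, without limits by limb, cause or planned status, and no analysis named in the plan suits freedom from MALE or deals with deaths that come first

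*Combined protocol and SAP*

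**What the plan says.** The only definition of MALE is in the Background, under Exercise Training Post-Revascularization. The text notes a lack of data on "amputation rates, readmission to hospital or reintervention rates in the PAD patients with critical limb ischemia" and continues: "Such parameters are defined as major adverse limb events (MALE".

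MALE is then used three times as an outcome:

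- Secondary outcome measures list "Freedom from MALE", with no components, start of follow-up or time point.
- Hypothesis 2 is comparative: the exercise group "will have fewer MALE and improved survival compared with patients treated with best medical therapy alone".
- Objective 2 names a different population. It is to "monitor major adverse limb events (MALE) and survival in patients who complete a 12-week SEP after revascularization".

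On timing, Methods (Intervention) says: "Patients will be approached regarding study participation prior to the revascularization procedure". It goes on: "After eligibility is confirmed and patients have signed informed consent, patients will be randomized to one of two groups". The revascularization is described next, together with "any adjunctive treatment such as wound care/debridement or minor amputation (toes, trans-metatarsal amputation". The Enrollment section instead has patients identified after revascularization, up to six months later, once wounds have healed sufficiently.

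Statistical Analysis names a paired t-test for baseline against 12 weeks and a Mann-Whitney test for non-normal data. Long-term Follow-up has annual contact for five years covering MALE and survival. Survival at 1, 3 and 5 years is a separate secondary outcome.

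**The concern.** Whoever classifies events has only the Background sentence to work from. It does not separate a major from a minor amputation, an index-limb event from a contralateral one, a planned procedure from an unplanned one, or a limb-related admission from any other. The Epidemiology section describes these patients as having multiple comorbidities, so some admissions will have nothing to do with the leg. On the Methods pathway, part of the index treatment also fits the literal wording.

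Three things are at stake. Events that exercise cannot change add to both arms and pull the contrast towards zero. The protocol quotes 10-40% one-year mortality in critical limb ischemia, so many patients may die before any MALE, and the plan does not say how they are counted. And an analysis limited to patients who complete the exercise program has no control arm and selects on something that happens after randomisation.

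**Working it through.** The documents give no event rate, sample size or power for MALE, so there is no planned figure to reproduce. The total of 64 patients is for walking distance. The steps below only show the size of the problem.

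**Inputs from the protocol**
- 61% with neither amputation nor re-intervention one year after bypass (Outcomes after revascularization). This leaves out readmission.
- One-year bypass limb salvage 88.5% (Table 2).
- One-year mortality 10-40% (Epidemiology).
- Three-year survival after angioplasty 68.4% (Table 2).
- 64 patients, taken as 32 per arm.

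**Assumptions not in the protocol**
- A share m = 10-40% of each arm has an index minor amputation.
- Exercise halves later events, equally in patients with and without an index amputation.
- Hazards are constant.

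**1. The definition moves the event rate.** Limb loss alone is 100 - 88.5 = 11.5% at one year. Any amputation or re-intervention is 100 - 61 = 39%, more than three times as many. The two figures come from different meta-analyses, and adding readmission would raise the second.

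**2. Dilution.** If a share m of both arms has an event that exercise cannot affect, the observed risk is p' = m + (1 - m)p. The observed difference is (1 - m) times the true one. With p = 39% against 19.5%:

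| m | Control | Exercise | Difference (points) | Risk ratio | Power, 32 per arm |
|---|---|---|---|---|---|
| 0 | 39.0% | 19.5% | 19.5 | 0.50 | 40% |
| 10% | 45.1% | 27.6% | 17.6 | 0.61 | 31% |
| 20% | 51.2% | 35.6% | 15.6 | 0.70 | 24% |
| 40% | 63.4% | 51.7% | 11.7 | 0.82 | 15% |

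Power is by normal approximation for two proportions, two-sided 0.05. Each 10% of patients affected adds about 6.4 such events among 64. The same formula applies to readmissions that exercise does not affect.

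**3. Deaths before MALE, at one year.** The MALE hazard is hM = -ln(0.61) = 0.494 per year. The death hazard hD runs from -ln(0.90) = 0.105 to -ln(0.60) = 0.511 per year.
- Deaths censored: 1 - exp(-0.494) = 39.0%.
- Cumulative incidence = hM/(hM + hD) × [1 - exp(-(hM + hD)t)].
- At 10% mortality: 0.494/0.600 × (1 - exp(-0.600)) = 37.2%.
- At 40% mortality: 0.494/1.005 × (1 - exp(-1.005)) = 31.2%.

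Censoring would therefore overstate one-year MALE by about 2 to 8 points. On the same model, 7.9% to 32.2% of patients die before any MALE, about 5 to 21 of 64.

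**4. Five years, as an extrapolation.** From Table 2, hD = -ln(0.684)/3 = 0.127 per year.
- Deaths censored: 1 - 0.61^5 = 91.6%.
- Cumulative incidence: 0.494/0.621 × (1 - exp(-0.621 × 5)) = 76%.

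The gap is about 16 points.

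**5. The two enrolment routes.** Under Methods, consent and randomisation come first and index minor amputation follows, so it falls inside any follow-up that starts at randomisation. Under Enrollment, the procedure and any index amputation come first, so it falls outside. The MALE clock is not defined on either route.

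**The case against.** The strongest reply is that the Background sentence describes a gap in the literature and is not an operating rule. It never says that every amputation or every readmission counts. It concerns the effects of exercise after treatment, and the protocol itself calls toe and transmetatarsal amputations minor and adjunctive. A reader might infer that the plan has decided to count index amputations as MALE. The documents do not support that: no time origin is stated, and on the Enrollment route these amputations precede randomisation. What stands is that no other definition exists and the two sections on timing disagree.

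A reader might also infer that mortality is ignored, or that the plan censors deaths. Neither is so. Survival is its own outcome and is followed for five years, and no method for MALE is prescribed at all. The gap is the missing rule for a patient who dies before MALE.

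It is tempting to carry 40% annual mortality to five years, which gives 91.6% against 48.9%, a gap of about 43 points. That implies 0.6^3 = 21.6% survival at three years, against 68.4% in Table 2. Constant event hazards are doubtful too: 88.5% limb salvage at one year would imply 0.885^3 = 69% at three years, where Table 2 has 82.3% for bypass. The five-year figure in the working uses the Table 2 death rate, but it still rests on a constant MALE hazard.

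Two more points stand. The documents do not show that readmissions would be mostly unrelated to the limb, or that exercise cannot affect cardiac admissions. And MALE is a secondary outcome in a pilot that claims no power for it.

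**Conclusion.** The concern holds as a gap in definition and analysis. A comparative hypothesis rests on one unqualified Background sentence, on sections that disagree about when randomisation happens, on an objective worded for exercise completers only, and on tests unsuited to an event-free outcome with deaths and incomplete follow-up.

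Dilution equals the share of patients with events that exercise does not affect. At an assumed 10-40%, a true risk ratio of 0.50 would appear as 0.61 to 0.82. These events fall on both arms equally in expectation, so they weaken the contrast and do not favour either arm, apart from chance imbalance in a small trial.

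If deaths were censored, one-year MALE would be overstated by about 2 to 8 points, and by roughly 16 points at five years as an illustration only. These figures describe the event rate within a group; no effect of competing death on the between-arm comparison has been shown. They use a bypass-only rate without readmission, and constant hazards.

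The point should be fixed before MALE is analysed. It does not touch the walking-distance outcome.

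**What to change.** In the outcome section:

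- List the MALE components and state the time origin.
- State that procedures planned as part of the index treatment are not events.
- Report hospital readmission as a separate outcome, split into limb-related and other.
- State whether later minor amputations and contralateral events count. The documents do not settle either, and both choices are defensible if made in advance.

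Reconcile Enrollment with Methods (Intervention) on whether randomisation comes before or after revascularization.

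In Statistical Analysis, compare the arms on MALE by cumulative incidence with death as a competing event, in all randomised patients, and read the result beside the survival outcome. Reword objective 2 to match.

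The cost is mainly wording, plus recording the date, limb, planned status and reason for each event. Fewer events will be counted, so intervals will be wider.

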Microsoft Excel will be used to generate a block randomization sequence for Phase I (20 patients) followed by a block randomization sequence for Phase II (44 patients) of the study. Patients who are eligible to participate in the study will be stratified by sex and randomized to either SEP or BMT. Block sizes of 4 and 6 will be used to prevent anticipation of the randomization sequence.

ALLOCATION CONCEALMENT

Once the random block sequence has been generated, allocation cards will be created and sealed in sequentially numbered opaque envelopes. The envelopes will be stored in a secured filing cabinet in the vascular surgery research office. The envelopes will be opened sequentially after a patient consents to participate in the study.

DATA COLLECTION

No study data will be collected until patients have reviewed and signed the informed consent. Opportunity to ask questions and have time independent from study team will be provided.

Data will be recorded using Excel spreadsheets. Medical outcomes and complications will be tracked using Vascubase software. Data will be stored on Alberta Health Services computers to maintain patient confidentiality.

STATISTICAL ANALYSIS

Normally distributed data will be presented as mean \pm SD. Results at baseline and 12 weeks will be compared using a paired t-test. For data that is not normally distributed, comparisons will be performed using a non-parametric Mann-Whitney test. Comparisons will be accepted as statistically significant at 95% confidence level ($p \leq 0.05$). STATA software will be used for statistical analysis.

ETHICAL CONSIDERATIONS

Patients who are randomized to the SEP group will be provided with tri-weekly visits for supervised exercise guidance and support. Patients will receive reimbursement for travel to and from the exercise facility. This will include refunds for gas, parking or other required transportation (taxi, public transport, etc).

FOLLOW UP OF PATIENTS WITHDRAWN FROM STUDY

Patients who withdraw or do not complete the program will be contacted and interviewed at the end of the 12 week study period to understand why they were unable to complete the training program.

LIMITATIONS

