One expected limitation of this study is the heterogeneity of the revascularization approach. Some patients will undergo endovascular treatment, while others will receive an open surgical bypass. Additionally, patients will not be stratified according to anatomical level of disease (aorto-iliac versus infrainguinal disease).

LONG-TERM FOLLOW-UP

This project is a pilot project with 12-week primary endpoint measures of functional capacity and quality of life. Given that we plan to extend to a broader randomized controlled clinical trial with long term follow-up, we will continue to follow the patients annually for five years. The annual follow-up will include QoL surveys, ABI measurements, ultrasound assessment for graft patency and any MALE. We will also monitor survival throughout this period.

REFERENCES

Adam, D. J., Beard, J. D., Cleveland, T., Bell, J., Bradbury, A. W., Forbes, J. F., . . . Storkey, H. (2005). Bypass versus angioplasty in severe ischaemia of the leg (BASIL): multicentre, randomised controlled trial. *Lancet*, 366(9501), 1925-1934. doi:10.1016/s0140-6736(05)67704-5

Agarwal, S. (2009). The association of active and passive smoking with peripheral arterial disease: results from NHANES 1999-2004. *Angiology*, 60(3), 335-345. doi:10.1177/0003319708330526

Badger, S. A., Soong, C. V., O'Donnell, M. E., Boreham, C. A., & McGuigan, K. E. (2007). Benefits of a supervised exercise program after lower limb bypass surgery. *Vasc Endovascular Surg*, 41(1), 27-32. doi:10.1177/1538574406296209

Bavry, A. A., Anderson, R. D., Gong, Y., Denardo, S. J., Cooper-Dehoff, R. M., Handberg, E. M., & Pepine, C. J. (2010). Outcomes Among hypertensive patients with concomitant peripheral and coronary artery disease: findings from the INternational VErapamil-SR/Trandolapril STudy. *Hypertension*, 55(1), 48-53. doi:10.1161/hypertensionaha.109.142240

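### The secondary objective limits MALE and survival to patients who complete the SEP, hypothesis 2 compares exercise participants with BMT, and no stated analysis population overrides the completer limit

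*Combined protocol and SAP*

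**What the plan says.** All references are to the combined protocol and SAP.

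- **Objectives.** The secondary objective is to "monitor major adverse limb events (MALE) and survival in patients who complete a 12-week SEP after revascularization". The primary objective, just above it, speaks of CLI patients after revascularization and has no completer limit.
- **Hypotheses.** Hypothesis 2 says that patients who participate in exercise rehabilitation "will have fewer MALE and improved survival compared with patients treated with best medical therapy alone". Its population is those who participate, not those who complete, and it names the comparator.
- **Outcome Measures.** The secondary outcomes include "Completion of a 12 week supervised exercise program" as an outcome in its own right. Freedom from MALE and "Survival at 1, 3 and 5 years" are listed with no limit to one arm or to completers.
- **Long-term Follow-up.** "we will continue to follow the patients annually for five years", with MALE and survival recorded and again no limit.
- **Statistical Analysis.** "Results at baseline and 12 weeks will be compared using a paired t-test", with a Mann-Whitney test for non-normal data. The section names no analysis population and no method for comparing MALE or survival between arms.
- **Follow up of Patients Withdrawn from Study.** Patients who withdraw or do not finish are interviewed at the end of the 12 weeks about their reasons. Whether they are analysed is not stated.

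**The concern.** The objective and its hypothesis name different populations, and the analysis section does not say which governs. An analyst who follows the objective as written has two options.

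1. Describe SEP completers alone. There is then no BMT comparator, and the result does not bear on hypothesis 2.
2. Join the objective to hypothesis 2 and compare SEP completers with all BMT patients. Completion happens after randomisation, and BMT patients cannot fail it because they have no programme to complete. The groups are then no longer those created by randomisation.

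Under the second option a patient who dies before the programme ends cannot be a completer. If survival is counted from the procedure or from study entry, such deaths stay in the BMT arm and disappear from the SEP arm. The resulting error favours exercise even when exercise does nothing.

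**Working it through.** The plan gives no figure for MALE or survival, so there is none to reproduce. The check below sizes the effect of the completer limit on survival. It is an illustration and not a forecast.

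**Inputs**
- Survival after angioplasty (Table 2): 98.3%, 92.3%, 87.0% and 74.3% at 1, 6, 12 and 24 months. Bypass survival is given as NA.
- Healing before the exercise assessment (Methods, Intervention): 1 to 6 weeks. With 12 weeks of SEP, completion falls at weeks 13 to 18 after the procedure.
- Total sample size 64 (20 + 44 over the two phases). Phase I is 1:1. Assuming the same for Phase II gives 32 per arm.
- No time origin is stated for survival. Enrollment describes identification within six months after the procedure, while Intervention describes an approach before it. Both clocks are therefore tried.

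**Assumptions.** No SEP effect, Table 2 angioplasty rates apply, and non-completion among survivors is unrelated to later death.

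**Formula.** If S(t) is survival to time t and c is the time of completion, completers show S(one year) / S(c), while all BMT patients show S(one year). The difference is the spurious gain.

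**Clock from the procedure**

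| Completion | Method | S(c) | 0.87 / S(c) | Gain, points |
|---|---|---|---|---|
| Week 13 | constant hazard, 0.87^(13/52) | 0.9658 | 0.9008 | +3.1 |
| Week 18 | constant hazard, 0.87^(18/52) | 0.9529 | 0.9130 | +4.3 |
| Week 13 (month 3.00) | interpolated, 98.3 − 2.00 × 1.2 | 0.9590 | 0.9072 | +3.7 |
| Week 18 (month 4.15) | interpolated, 98.3 − 3.15 × 1.2 | 0.9452 | 0.9205 | +5.0 |

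The slope of 1.2 points per month is (98.3 − 92.3) / 5. Expected deaths before completion among 32 SEP patients run from 32 × (1 − 0.9658) = 1.1 to 32 × (1 − 0.9452) = 1.8.

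**Clock from entry**, with one year counted from entry, 12 weeks = 2.77 months, and Table 2 interpolated linearly:

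| Entry after procedure | Alive at 12 weeks | Alive at one year, all | Completers | Gain, points |
|---|---|---|---|---|
| Month 1 | 0.9662 | 0.8743 | 0.9049 | +3.1 |
| Month 3 | 0.9653 | 0.8741 | 0.9055 | +3.1 |
| Month 6 | 0.9735 | 0.8738 | 0.8976 | +2.4 |

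**Clock from week 12 in both arms.** Deaths before week 12 are outside the comparison in both arms. Under the stated assumption on survivors, the gain is 0.

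**Yardstick.** The standard error of a difference at 87% with 32 per arm is sqrt(2 × 0.87 × 0.13 / 32) = 0.084, or 8.4 points.

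**Sensitivity.** The Epidemiology section gives one-year CLI mortality of 10 to 40%. With a constant hazard and the procedure clock:
- At 10%: 0.9^(39/52) − 0.9 = +2.4 points and 0.9^(34/52) − 0.9 = +3.3 points.
- At 40%: 0.6^(39/52) − 0.6 = +8.2 points and 0.6^(34/52) − 0.6 = +11.6 points. The standard error at 60% survival is sqrt(2 × 0.6 × 0.4 / 32) = 0.122, or 12.2 points.

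The gain stays below one standard error in these cases too.

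**The case against.** The strongest reply is that this is one loosely worded sentence. The primary objective also leaves out BMT, and nobody would take it to describe a single arm. The objectives name the experimental treatment and the hypotheses supply the comparator. The trial is randomised with two arms, the outcome list is unrestricted, and follow-up covers the patients in general. This largely stands. A reader might infer that BMT patients will not be followed for MALE and survival, or that hypothesis 2 cannot be tested. The documents do not support that: both arms' data will probably exist, and the hypothesis can be tested with them.

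A reader might also infer that the sponsor plans to compare SEP completers with all BMT patients. No section says so. That comparison arises only when the objective's population is joined to the hypothesis, and no section says that non-completers are dropped. It is a risk that the wording leaves open and not a stated plan.

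It is also true that the trial is sized on the 6-minute walk, that the Phase II objectives in Study Design name walking distance and quality of life but not MALE or survival, and that the missing analysis population affects every endpoint. These points limit the weight of the concern.

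What survives is narrow. The unrestricted passages concern which data are collected. None defines who is analysed, and the only stated population for this objective is the completers.

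**Conclusion.** The point holds as a mismatch between the secondary objective and hypothesis 2 that the analysis section does not resolve. It should be corrected, but it does not show that the trial cannot answer its question.

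If the completer limit were applied against all BMT patients, the spurious one-year survival gain would be about 2 to 5 points under Table 2 angioplasty rates with time from the procedure or from entry. It would be zero with time from week 12 in both arms and survivors' non-completion unrelated to later death. It rests on one or two early deaths among 32 patients and is below one standard error. The enrolled patients are independent, ambulatory and cleared by their surgeon, so they may die less often than Table 2 suggests, which would shrink the gain. If survivors who do not complete are sicker, it would grow. The higher mortality used as a sensitivity case is for CLI in general and need not apply here.

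A reader might carry the same arithmetic over to MALE. The documents do not support a figure there: the bias depends on patients with a limb event completing less often than event-free patients, and nothing is said about that.

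Though small against the noise, the error would be systematic and in the direction of the hypothesis. It matters beyond this pilot because Long-term Follow-up says a broader randomised trial is planned.

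**What to change.** - **Objectives.** Reword the secondary objective so that MALE and survival are compared between the SEP and BMT arms in all randomised patients, by assigned arm, from one common time origin that is named.
- **Statistical Analysis.** State that this as-randomised analysis is primary for MALE and survival, and that any analysis of completers is supportive.
- **Follow up of Patients Withdrawn from Study.** State that patients who stop the programme without withdrawing consent stay in the 12-week assessment and the annual follow-up already planned.

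The cost is wording only, with no visits or patients beyond those planned. The small downside is that an as-randomised estimate is diluted by non-adherence. The supportive completer analysis can be shown beside it, with its limits stated.
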